#### **4.6.1.5      Laboratory Assessments**

Normal ranges for the study laboratory parameters must be supplied to the Sponsor before the study starts. Laboratory safety tests shall be collected at time-points specified in the Schedule of Assessments ([Appendix 1](#)).

Additional blood or urine samples may be taken at the discretion of the Investigator if the results of any test fall outside the reference ranges, or clinical symptoms necessitate additional testing to monitor healthy volunteer's safety. Where the clinical significance of abnormal lab results is considered uncertain, screening lab tests may be repeated before randomization to confirm eligibility. If there is an alternative explanation for a positive urine test for drugs of abuse, e.g., previous occasional intake of a medication or food containing for example codeine, benzodiazepines or opiates, the test could be repeated to confirm washout.

In the event of unexplained abnormal clinically significant laboratory test values, the tests should be repeated immediately and followed up until they have returned to the normal range and/or an adequate explanation of the abnormality is found. Results of clinical laboratory testing will be recorded on the eCRF or be received as electronically produced laboratory reports submitted directly from the local or central laboratory.

Samples for the following laboratory tests will be sent to one or several laboratories or to the Sponsor for analysis. Instruction manuals and supply kits will be provided for all laboratory assessments.

- Hematology: Hb, hematocrit, total WBC count, differential WBC count (including basophils, eosinophils, lymphocytes, monocytes and neutrophils), platelet count, red blood cells count, mean corpuscular volume, mean corpuscular hemoglobin, mean corpuscular hemoglobin concentration and reticulocyte (%) counts.
- Coagulation: INR and aPTT.
- Blood chemistry: ALT, AST, total and indirect bilirubin, alkaline phosphatase (ALP), gamma glutamyl transpeptidase (GGT; only at Screening), total protein, albumin, urea, creatinine, uric acid, total cholesterol, triglycerides, glucose, sodium, chloride, potassium, calcium, phosphorus, bicarbonate, cystatin C, HbA1c (only at Screening).
- Urinalysis: A midstream, clean-catch urine specimen will be collected for dipstick analysis of protein, blood, glucose, leucocytes and pH. If the dipstick result is 2+ or greater for blood, protein or leukocytes, urine will be sent to the laboratory for microscopy. If there is an explanation for the positive dipstick result, e.g., menses, it should be recorded, and there is no need to perform microscopy.
- Substance use: Drugs of abuse urine test and alcohol test (only at Screening and Day – 1). A breath test may be used to test for alcohol.
- Viral serology (only at Screening):

HIV

HAV Ab IgM

HBsAg

HCV Ab

- Pregnancy test:

Serum or plasma beta-human chorionic gonadotropin ( $\beta$ -HCG) at Screening, urine on all other occasions (females only).

- Hormones (only at screening): follicle-stimulating hormone (females only to confirm post-menopausal status).
- Thyroid function tests (only at screening): TSH, free T3 and free T4.
- Autoimmune panel (only at screening): ANA, AMA, ASMA and thyroid peroxidase antibody.

Based on continuous analysis of the data in this study and other studies, any sample type not considered to be critical for safety may be stopped at any time if the data from the samples collected does not produce useful information.

#### **4.6.1.6 Pharmacokinetic Assessments**

Blood and urine (SAD only) samples for determination of plasma and urine concentrations of RO7020531, the main active metabolite RO7011785, and additional

metabolites (as applicable) including RO7018822 and RO7033805, will be collected at time-points specified in the SoA ([Appendix 1](#), [Appendix 2](#), [Appendix 3](#) and [Appendix 4](#)).

RO7020531, RO7011785, RO7018822 and RO7033805 plasma and urine concentrations will be measured by a specific and validated method. The plasma PK parameter will be read directly from the plasma concentration versus time profiles, or calculated using standard non-compartmental methods. Total drug concentrations of RO7020531, the main active metabolite RO7011785, and additional metabolites (as applicable) including RO7018822 and RO7033805, will be calculated over a 24-hour interval.

The volume and pH of urine voided at each interval will be recorded and aliquots will be collected from the pooled samples at each time interval for analysis.

Details on sampling procedures, sample storage, and shipment are given in the Laboratory Manual.

#### **4.6.1.7 Pharmacodynamic Assessments**

Blood samples will be collected to evaluate a number of PD parameters including the protein and metabolite markers of humoral response (IFN- $\alpha$ , IP-10, TNF- $\alpha$ , IL-6, IL-10, IL-12p40, and neopterin) *and markers of transcriptional responses (ISG15, OAS-1, MX1 and TLR7)*.

Instruction manuals and supply kits will be provided for the collection of all PD samples.

Time-points of PD blood sample collection are provided in the SoA ([Appendix 1](#), [Appendix 2](#), [Appendix 3](#) and [Appendix 4](#)).

These samples will be stored for up to 5 years for the protocol assessments defined above, unless otherwise indicated. Samples will be destroyed no later than 5 years after the date of final closure of the clinical database, unless Regulatory Authorities require specimens to be maintained for a longer time period.

#### **4.6.1.8 Clinical Genotyping**

Instruction manuals and supply kits will be provided for the collection of all biomarker samples. One blood sample will be collected before first intake of drug. If sample collection was missed, it can be collected at any time thereafter. Collection time is provided in the SoA ([Appendix 1](#), [Appendix 2](#), [Appendix 3](#) and [Appendix 4](#)). Data arising from all biosamples will be subject to the confidentiality standards described in Section [8.4](#).

These samples will be stored for up to 5 years for the protocol assessments defined above, unless otherwise indicated. Samples will be destroyed no later than 5 years after the date of final closure of the clinical database, unless Regulatory Authorities require specimens to be maintained for a longer time period.

## **4.6.2        Timing of Study Assessments**

### **4.6.2.1      Screening and Pretreatment Assessments**

Written informed consent for participation in the study must be obtained before performing any study specific screening tests or evaluations. Informed Consent Forms for enrolled healthy volunteer and for healthy volunteers who are not subsequently enrolled will be maintained at the study site.

All screening and pre-treatment assessments must be completed and reviewed to confirm that healthy volunteers meet all eligibility criteria. The Investigator will maintain a screening log to record details of all healthy volunteers screened and to confirm eligibility or record reasons for screening failure.

An Eligibility Screening Form (ESF) documenting the Investigator's assessment of each screened healthy volunteer with regard to the protocol's inclusion and exclusion criteria is to be completed by the Investigator and kept at the investigational site.

A screening examination should be performed from Day -28 to Day -2 for SAD and MAD parts of the study. Subjects must fulfill all entry criteria to be accepted into the study. Assessments as detailed in the SoA ([Appendix 1](#), [Appendix 2](#), [Appendix 3](#) and [Appendix 4](#)) will be conducted.

### **4.6.2.2      Assessments during Treatment**

Under no circumstances will healthy volunteers who enroll in this study and have completed treatment as specified, be permitted to be allocated a new randomization number and re-enroll in the study.

All assessments must be performed as per SoA ([Appendix 1](#), [Appendix 2](#), [Appendix 3](#) and [Appendix 4](#)).

### **4.6.2.3      Follow Up Assessments**

Healthy volunteers who complete the study (SAD and MAD parts) or discontinue from the dosing early (MAD part only) will be asked to return to the clinic approximately 7 days ( $\pm 1$  day) after the last dose of study drug for a follow-up visit and will be contacted for a follow-up call approximately 21 days ( $\pm 3$  days) after the follow-up visit to complete assessments as specified in the SoA ([Appendix 1](#), [Appendix 2](#), [Appendix 3](#) and [Appendix 4](#)). After the follow-up call, adverse events should be followed as outlined in Section [5.5](#), Section [5.6](#).

### **4.6.2.4      Assessments at Unscheduled Visits**

If an unscheduled visit is required for safety reasons, necessary assessments will be undertaken at the discretion of the Investigator. All unscheduled assessments should be reported in eCRF.

In case of early termination of a subject in MAD part, a blood sample for PK assessment may be collected at the time of discontinuation.

## **4.7           HEALTHY VOLUNTEER, STUDY, AND SITE DISCONTINUATION**

### **4.7.1       Healthy Volunteer Discontinuation**

The Investigator has the right to discontinue a healthy volunteer from RO7020531 or withdraw a healthy volunteer from the study at any time. In addition, healthy volunteers have the right to voluntarily discontinue study drug (MAD part only) or withdraw from the study at any time for any reason. Reasons for discontinuation of study drug or withdrawal from the study may include, but are not limited to, the following:

- Healthy volunteer withdrawal of consent at any time.
- Any medical condition that the Investigator or Sponsor determines may jeopardize the healthy volunteer's safety if he or she continues in the study.
- Investigator or Sponsor determines it is in the best interest of the healthy volunteer.
- Healthy volunteer non-compliance.

Healthy volunteers in the MAD part of the study who discontinue study treatment due to poor tolerability to study drug, or other safety-related reasons will not be replaced.

Healthy volunteers who discontinue study treatment early for non-safety reasons may be replaced to ensure sufficient data to make dose-escalation and drug development decisions.

The decision to replace a subject will be made by a mutual agreement between the Sponsor and Investigator.

#### **4.7.1.1      Discontinuation from Study Drug during MAD**

For an individual subject in the MAD part of the study, dose continuation will not occur if the subject experiences any of the following:

- Clinically significant RO7020531-related changes in safety parameters that are considered not acceptable by the Investigator and/or the Sponsor; or
- Poor tolerability, which is considered to affect the healthy volunteer's well-being and/or the PK evaluation.
- Pregnancy.

Healthy volunteers who discontinue study drug prematurely will be asked to return to the clinic within 7 days for a follow-up visit to complete follow-up assessments

(Section 4.6.2.3). The primary reason for premature study drug discontinuation should be documented on the appropriate eCRF. Healthy volunteers who discontinue study drug prematurely for safety reasons will not be replaced.

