between species and influenced the concentrations of the different intermediate prodrugs: RO7033805 was the predominant intermediate for cynomolgus monkey, whereas RO7018822 was the predominant intermediate for mouse, rat, and human.

RO7020531 was found to be a good substrate of multidrug resistance protein 1 (MDR1; P-glycoprotein), with a high apparent membrane permeability. Therefore, *in vivo* drug-drug interactions due to co-administration with MDR1 inhibitors cannot be excluded. However, interactions of strong MDR1 inhibitors with the absorption of RO7020531 are considered unlikely due to the high permeability, high solubility, and high oral bioavailability of RO7020531, which makes it unlikely that MDR1 plays a major role in RO7020531 trans-intestinal absorption *in vivo*.

RO7011785 can be directly glucuronidated by UDP-glucuronosyltransferase 1A1 (UGT1A1); thus, drug-drug interactions with UGT1A1 inhibitors cannot be excluded. Drug-drug interaction potential was low, as determined *in vitro* with cytochrome P450 (CYP) enzymes and with transporters (organic anion transporting polypeptide 1B1 [OATP1B1], OATP1B3, organic anion transporter 1 [OAT1], OAT3, and breast cancer resistance protein [BCRP]). Therefore, the interactions with CYPs and substrates for hepatic uptake transporters and kidney transporters (for example NUCs) *in vivo* are unlikely.

Repeat-dose toxicity studies with treatment duration of up to 13 weeks have been performed with RO7020531 in rats and monkeys. The effects observed were considered to be consistent with exaggerated pharmacology, i.e., TLR7 agonism leading to the intended immune/cytokine stimulation and subsequent tolerability or pro-inflammatory findings. QOD and QW dosing regimens were investigated in Good Laboratory Practice (GLP) toxicology studies. The no-observed-adverse-effect level (NOAEL) for the 13-week rat toxicology study was 3 mg/kg QOD (area under the concentration–time curve for males and females  $AUC\ M/F = 186/503\ h \cdot ng/mL$ ) and 30 mg/kg QW ( $AUC\ M/F = 2950/4660\ h \cdot ng/mL$ ). The NOAEL for the 13-week monkey toxicology study was 3 mg/kg QOD ( $AUC\ M/F = 858/706\ h \cdot ng/mL$ ) and 10 mg/kg QW ( $AUC\ M/F = 3340/2960\ h \cdot ng/mL$ ).

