### **3.1.1.2      Multiple Ascending Dose Study**

The trigger to start the first cohort in the MAD includes documentation of adequate safety and tolerability in the SAD cohorts and evidence of PD effects. For a given dose evaluated in the SAD, evidence in at least two subjects exhibiting responses above placebo-defined baseline for select PD biomarkers, including *the protein and metabolite markers IFN- $\alpha$ , IP-10, TNF- $\alpha$ , IL-6, IL-10, IL-12p40 and neopterin and markers of transcriptional responses (ISG15, OAS-1, MX1 and TLR7)*, should be demonstrated. If the next dose in the SAD has been considered safe, then the previous dose demonstrating TLR-associated PD activity will be considered as the starting dose for the MAD. In addition, the starting dose/exposure in the MAD part of this study should have been considered safe in the global EIH study (NP39305). Only doses covered by the dose range evaluated in the SAD part will be used in the MAD, and two to three dose levels will be evaluated (Figure 1).

[figure not shown]
Once criteria have been reached to determine an initial dose for MAD, subjects will be screened up to 28 days before enrollment into the MAD part of this study. They will be asked to remain in the unit from Day -2 until Day 14 with QOD dosing initiated on Day 1. In total, 7 QOD doses will be administered with the last dose given on Day 13. Subjects will be discharged on Day 14. After completing 7 QOD doses, each subject in the MAD cohorts will return for an outpatient follow-up visit 7 days after the last dose. All subjects will have a follow-up phone call 28 days after their last dose. Subjects will be asked to report any AEs that occur during this period.

Upon safety review of the MAD cohort(s) data, dose escalation will proceed in the MAD part of this study. The maximum dose investigated in MAD will not exceed doses

evaluated in the SAD part of this study nor will it exceed doses and exposures considered to be safe and with acceptable tolerability in the global EIH study.

Based on the PK, PD and safety evaluation of the previous dose cohorts, additional cohorts of subjects may be enrolled at higher or lower dose levels, or at a dose level already tested.

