## **3.2 RATIONALE FOR STUDY DESIGN**

### **3.2.1 Rationale for Dosage Selection and Dosage Regimen**

The dose selection for this study is supported by the non-clinical safety data and may be modified based on the clinical data collected from the global EIH study, NP39305. The current study in Chinese healthy volunteers (YP39553) is planned to consist of four to six dose levels in SAD and two to three dose levels in MAD, which will be within the dose-range considered to be safe and with acceptable tolerability in the global EIH study, NP39305.

Based on the non-clinical data with RO7020531 (see Section 1.2.1), the half-life of the active TLR7 agonist RO7011785 is relatively short. However, previous experience in monkeys and humans with another TLR7 agonist (RO6864018) indicate that a short exposure of the TLR7 agonist initiates a series of pharmacodynamic events with biomarker activity that peaks as late as 48 hours post dose. Similar results are

anticipated following dosing with RO7020531 and are supported by activity measured in non-clinical models.

*In the ongoing global EIH study (NP39305), all dose levels tested in SAD (3 mg – 170 mg) have been observed to be safe and well tolerated. In SAD Cohort 6 (100 mg), 3/8 healthy volunteers demonstrated increases in interferon alpha and which met the predefined criteria for TLR7 marker activity.*

The starting dose of 40 mg was selected for the SAD portion of this study in Chinese patients based on the safety and tolerability documented in the study NP39305, avoiding very low doses/exposures that may not produce pharmacodynamic effects, while ensuring appropriate safety margins expected with the first dose.

The phenomena of response priming (increase in PD effects with the second dose) and tachyphylaxis (reduced response with chronic and frequent doses) are expected with RO7020531 based on clinical and non-clinical data observed with another TLR7 agonist, RO6864018. The phenomenon of TLR7 priming was frequently observed with RO6864018 in cynomolgus monkeys after the second dose administration and was followed by a subsequent response tachyphylaxis. Similarly, in healthy volunteers and HCV patients (Study ANA773-601), there is evidence of response priming with QOD schedule of RO6864018 showing an increase in PD response with the second dose, and evidence of tachyphylaxis to systemic IFN with repeated dosing on QOD schedule.

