### **5. ASSESSMENT OF SAFETY**

#### **5.1 SAFETY PARAMETERS AND DEFINITIONS**

Safety assessments will consist of monitoring and recording adverse events, including serious adverse events and non-serious adverse events of special interest; measurement of protocol-specified safety laboratory assessments; measurement of protocol-specified vital signs, ECGs; and other protocol-specified tests that are deemed critical to the safety evaluation of the study.

Certain types of events require immediate reporting to the Sponsor, as outlined in Section [5.4](#).

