### Appendix 3 Schedule of Assessments: MAD

Visit	Screening	Treatment Period															Follow Up Visit	Follow Up Call
Day	D-28 to D-2	Day -1	Day 1	Day 2	Day 3	Day 4	Day 5	Day 6	Day 7	Day 8	Day 9	Day 10	Day 11	Day 12	Day 13	Day 14	Day 20 a	Day 41 b
Informed Consent	X																	
Eligibility	X	X																
Demography	X																	
Medical History	X																	
Physical Examination c	X	X								X							X	X
Vital Signs d	X	X	6	X	4	X	2	X	2	X	2	X	2	X	6	X	X	
ECG-12 lead e	X	X	6		3				X						6		X	
Plasma PK Sample			12	X	3	X	3	X	3	X	3	X	3	X	12	X		
PD for Protein Biomarkers		X	4	X	3	X	3	X	3	X					3	X	X	
Whole Blood for RNA		X	4	X	3	X	3	X	3	X					3	X	X	
Hematology, Blood Chemistry, Coagulation, Urinalysis	X	X				X				X			X		X	X	X	
Pregnancy Test f	X	X															X	
Administration of Study Medication g			X		X		X		X		X		X		X			
In-Clinic Stay h		X	X	X	X	X	X	X	X	X	X	X	X	X	X	X		
Ambulatory Visit	X																X	
Randomisation			X															
Autoimmune panel, Thyroid function	X																	
Viral Serology ( HAV, HBV, HCV, HIV)	X																X	
Follicle Stimulating Hormone i	X																	
Substance Use j	X	X																
Clinical Genotyping k			X															
Adverse Events	X l	X l	X	X	X	X	X	X	X	X	X	X	X	X	X	X	X	
Previous and Concomitant Treatments	X	X	X	X	X	X	X	X	X	X	X	X	X	X	X	X	X	

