## Appendix 4 Schedule of Assessments: MAD Detailed (cont.)

- a) Vital signs include blood pressure, pulse rate, respiratory rate and body temperature. Blood pressure, respiratory rate and pulse rate will be obtained after the subject has been in a supine *or sitting* position for at least 5 minutes. Blood pressure measurement will be performed in triplicate (can be as short as 20-second to 1-minute interval between measurements). Pulse rate and body temperature measurement will be performed as single assessments.
- b) 12-lead ECGs will be obtained in triplicate (three consecutive interpretable 12-lead ECGs within a 2-5 minute interval) after the subject has been in a supine position for at least 10 minutes. Automated ECG intervals (PR (PQ), QRS, QT, QTcF) and HR will be captured or calculated, and the changes in T-wave and U-wave morphology will be documented.
- c) Plasma PK samples will be collected: pre-dose and 0.25, 0.5, 1, 1.5, 2, 3, 4, 6, 8, 12, 18 and 24 post-dose from Day 1 to Day 2 and from Day 13 to Day 14. On Days 3, 5, 7, 9, and 11, samples for PK will be taken at pre-dose and 2, 6 and 24 hours post-dose.
- d) PD samples will be collected: pre-dose and 2, 6, 12 and 24 post-dose from Day 1 to Day 2. On Days 3, 5, 7 and 13 samples for PD will be taken at pre-dose and 2, 6 and 24 hours post-dose. PD samples will be collected on follow-up visit.
- e) If the clinical genotyping blood sample is not collected at Day 1, it may be collected at any time during the conduct of the clinical study.
- f) Study drug will be administered in fasted state (after an overnight fast of at least 10 hours).
- g) A follow-up visit to be completed 7 days ( $\pm 1$ ) after the last dose of study medication.

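### In the MAD no safety laboratory test is scheduled between Day -1 and Day 4, so the individual dose-continuation rule has no scheduled on-treatment laboratory result before the second dose

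*Combined protocol and SAP*

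**What the plan says.** **The rule.** Section 4.7.1.1, repeating Section 3.1.3, states that dosing will not continue in an individual MAD subject who experiences "Clinically significant RO7020531-related changes in safety parameters that are considered not acceptable by the Investigator and/or the Sponsor". Section 5.1 includes "measurement of protocol-specified safety laboratory assessments" among the safety assessments. Section 5.3.5.4 foresees a laboratory result leading to discontinuation of treatment. Section 5.2.1 rules out dose modification for safety in the MAD, so discontinuation is the individual action on dosing that remains.

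**The dosing.** Section 3.1.1.2: "In total, 7 QOD doses will be administered with the last dose given on Day 13". The doses fall on Days 1, 3, 5, 7, 9, 11 and 13.

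**The laboratory schedule.** The Appendix 3 row "Hematology, Blood Chemistry, Coagulation, Urinalysis" is marked at Screening and on Days -1, 4, 8, 11, 13, 14 and 20. Appendix 4 agrees, and places the Day 11 and Day 13 draws before the dose. Neither table marks a safety laboratory test on Day 1, on Day 2 or before the Day 3 dose.

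**What is collected before dose 2.** Appendix 4 has vital signs and blood for PK, protein PD and RNA at 24 h on Day 2. Before the Day 3 dose it has vital signs, ECG and the same blood samples.

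**The SAD.** Appendices 1 and 2 schedule safety laboratory tests 24 h after the single dose and again on Day 8.

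**Expected response.** For RO7020531, Section 3.2.1 anticipates "The phenomena of response priming (increase in PD effects with the second dose) and tachyphylaxis", on the strength of data with another TLR7 agonist.

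**The concern.** The stop rule covers laboratory changes, but the schedule gives it no laboratory data at the first point where it could apply. A subject with a clinically significant but symptomless laboratory change after dose 1 would receive dose 2 before any scheduled test could show it.

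There is also a cost in interpretation. Safety is the primary objective, and the incidence of laboratory abnormalities is a named outcome (Section 3.3.1). The first on-treatment MAD result comes after two doses, so a first-dose laboratory effect cannot be separated from a second-dose one. The MAD also has no 24 h first-dose result to set beside the SAD.

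The gap stands out because dose 2 is the dose at which Section 3.2.1 expects a larger PD effect.

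**Working it through.** The plan gives no figure on this point, so the check is a timeline count.

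**Inputs.** Dosing days and laboratory days come from Appendix 3, and draw times from Appendix 4. Time zero is dose 1, and dose *k* is given at 48 × (*k* − 1) hours.

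| Dose | Day | Hours from dose 1 | Last scheduled laboratory draw | Draw since previous dose |
|---|---|---|---|---|
| 1 | 1 | 0 | Day -1 | not applicable |
| 2 | 3 | 48 | Day -1 | none |
| 3 | 5 | 96 | Day 4 | Day 4 |
| 4 | 7 | 144 | Day 4 | none |
| 5 | 9 | 192 | Day 8 | Day 8 |
| 6 | 11 | 240 | Day 11 pre-dose | Day 11 pre-dose |
| 7 | 13 | 288 | Day 13 pre-dose | Day 13 pre-dose |

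**Results.**
- Two of the six repeat doses (2 and 4) have no scheduled draw since the preceding dose. Only dose 2 has no on-treatment result at all.
- The Day 4 draw is at (4 − 1) × 24 = 72 h from dose 1 and 72 − 48 = 24 h from dose 2. It is 96 − 72 = 24 h before dose 3, so it can inform that dose.
- Dose 4 relies on a draw taken 144 − 72 = 72 h earlier, before dose 3 was given.
- MAD subjects: 2 × 10 to 3 × 10 = 20-30. On active drug: 2 × 8 to 3 × 8 = 16-24.

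**Whether other text fills the gap.**
- Section 4.6.1 names safety blood tests only in a rule on the order of coinciding pre-dose assessments. It adds no draw.
- Section 4.6.1.5 allows extra samples at the investigator's discretion when a result is out of range or symptoms call for testing. A silent change after dose 1 triggers neither.
- Section 4.6.2.4 covers unscheduled visits needed for safety reasons, which also presupposes a reason.
- Sentinel dosing is described only for the single-dose cohorts (Section 3.1.1.1).
- Section 4.2 bars re-randomization to another cohort, so a MAD subject has no earlier on-drug laboratory result from this study.

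The cohort escalation decision is a separate matter. Section 3.1.2 bases it on MAD safety data through Day 14, by which time several draws exist.

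**The case against.** The strongest reply is that nothing here contradicts itself. The two appendices agree, and the rule does not promise a laboratory test before every dose. It can act on the other safety parameters, and adverse events, vital signs and an ECG are all available before dose 2 in subjects who stay in the unit. That stands: this is a gap between a rule and its data, not an inconsistency between tables.

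Second, first-dose laboratory effects are studied at group level before the MAD begins. A SAD dose becomes a candidate MAD starting dose only if the next SAD dose was considered safe. MAD doses may not exceed those evaluated in the SAD, nor doses and exposures considered safe in the global study (Section 3.1.1.2). Section 1.2.2 reports no clinically significant laboratory changes or trends there after single doses of 3 to 170 mg. This lowers the risk. It does not give the individual rule a result for the individual subject.

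Third, Day 4 is a reasonable time to test: 24 h after the dose expected to be primed and before dose 3. That also stands, and a reader who infers that laboratory changes from dose 1 can never be acted on would be wrong.

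A reader might also infer that dose 2 is expected to be more toxic. The documents do not support this. Section 3.2.1 describes priming of PD effects, carried over from another agonist, and adds that tachyphylaxis follows. The same section suggests that the QOD schedule may limit adverse events. Section 1.2.1 links "TLR7 agonism leading to the intended immune/cytokine stimulation and subsequent tolerability or pro-inflammatory findings", but for repeat-dose animal studies of up to 13 weeks. No section says that laboratory toxicity is primed.

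Finally, one might suspect that the same-day pre-dose results for doses 6 and 7 would arrive too late. The documents give no turnaround time, so nothing here rests on that.

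**Conclusion.** The point holds in limited form. Before dose 2 the individual rule has no scheduled on-treatment laboratory result, and before dose 4 it has none since dose 3. This applies to every MAD subject. The first MAD result mixes two doses, so the 24 h first-dose comparison with the SAD is lost; a comparison of the second dose with a single dose at 24 h remains possible, subject to carry-over.

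The exposed case is narrow: an asymptomatic, clinically significant laboratory change after dose 1 or dose 3. The documents give no probability for it, and the existing safeguards reduce it without removing it. The counts of 20-30 and 16-24 are people on this schedule, not expected events.

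The conclusion assumes that the appendix tables show the full laboratory schedule, which their agreement supports, and that safety parameters in the rule carry the meaning of Section 5.1. It is a cheap improvement, not a defect that undermines the study.

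**What to change.** Reconcile the laboratory schedule in Appendices 3 and 4 with the individual rule in Sections 3.1.3 and 4.7.1.1, so that the protocol makes clear what laboratory information, if any, that rule has before dose 2, and likewise before dose 4.

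A low-cost way to close the dose 2 gap is to collect the safety blood tests (hematology, chemistry, coagulation) at the Day 2 24 h draw already scheduled for PK and PD. This would also supply a first-dose 24 h result matching the SAD. How the result bears on dosing is for the sponsor and investigator to decide.

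The cost is one extra set of routine tubes per MAD subject (20-30 sets) at an existing venepuncture, a small added blood volume, the laboratory and review work, and a schedule amendment. The Day 2 draw does not address dose 4, which needs its own answer in the reconciliation.
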